This proposal will directly assess the effect of glucagon on rates of hepatic mitochondrial oxidation and pyruvate carboxylase flux in humans for the first time using Positional Isotopomer NMR Tracer Analysis (PINTA) (Perry et al. **Nature Communications** 2017). The results of these studies have important implications for the possibility of intervening in the pathogenesis of NAFLD-associated hepatic insulin resistance and T2D via chronic dual glucagon-like peptide-1/glucagon receptor agonism and provide an important rationale for why a dual agonist might be more efficacious for treating NAFLD/NASH/T2D than GLP-1 alone.

Objectives

- List the objectives to correspond directly with the listed hypotheses:

To examine the effects of glucagon on hepatic glucose and fat metabolism *in vivo*, we plan to apply a novel Positional Isotopomer NMR Tracer Analysis (PINTA) method to quantify rates of hepatic mitochondrial oxidation (V_{CS}) and pyruvate carboxylase flux (V_{PC}), which has been cross-validated in awake rodents and humans (Perry et al. **Nature Communications** 2017). In preliminary rodent studies we have found that glucagon stimulates intrahepatic lipolysis through an $InsP_3R$ -I-dependent process, leading to increases in hepatic acetyl-CoA content, which allosterically activates pyruvate carboxylase activity and flux (V_{PC}), and that this phenomenon explains its acute, transcription-independent effect to acutely stimulate hepatic gluconeogenesis *in vivo* (unpublished results). In addition, using PINTA analysis we found that glucagon stimulates hepatic mitochondrial oxidation (V_{CS}) through $InsP_3R$ -I-mediated calcium signaling in awake mice, and that this process can be exploited by short-term continuous glucagon treatment leading to two-fold increases in hepatic mitochondrial fat oxidation (V_{FAO}), which in turn results in large reductions in hepatic steatosis and marked improvements in glucose tolerance through reversal of hepatic insulin resistance in a high fat fed rat model of NAFLD.

Hypothesis

- List the clinical Hypotheses in order of priority:

1. A physiological increase in plasma glucagon concentrations will promote a significant increase in rates of hepatic mitochondrial oxidation (V_{CS}) in healthy humans.
2. A physiological increase in plasma glucagon concentrations will promote a significant increase in rates of hepatic pyruvate carboxylase flux (V_{PC}) in healthy humans.

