3. A physiological increase in plasma glucagon concentrations will promote a significant increase in rates of $^{13}C_4$ β -OHB turnover (hepatic ketogenesis) in healthy humans.

Study Design/Clinical Plan

- Provide a concise overview stating the type of experimental design

The effects of a physiological increase in plasma glucagon on rates of hepatic mitochondrial oxidation and pyruvate carboxylase flux will be examined in 12 healthy subjects (ages 21-65) using Positional Isotopomer NMR Tracer Analysis (PINTA) (Perry et al. **Nature Communication** 2017). Briefly rates of hepatic mitochondrial oxidation (V_{CS}) and hepatic pyruvate carboxylase flux (V_{PC}) will be assessed in 12 healthy overnight fasted subjects by PINTA after a three-hour infusion of glucagon or saline. The glucagon infusion [3 ng/(kg-min)] will be designed to increase peripheral and portal vein plasma glucagon concentrations 3-4 fold. The effects of a physiological increase in plasma glucagon on rates of hepatic ketogenesis will also be assessed using an infusion of $^{13}C_4$ β -OHB (Perry et al. **Cell Metabolism** 2017).

Rates of hepatic pyruvate carboxylase flux (V_{PC})/citrate synthase flux (V_{CS}) by PINTA: Subjects (n=12) will be studied by PINTA under 2 conditions: 1) at 0700 following an overnight (12h) fast and a 3h saline infusion (Control), 2) at 0700 following an overnight (12h) fast and a 3h glucagon infusion @ [3 ng/(kg-min)] (Glucagon Rx). Briefly, on the morning of the study an IV line will be inserted into an antecubital vein for infusions and second IV line will be inserted retrogradely into a hand vein for blood collections. The hand will be warmed in a 'hot box' to arterialize the blood. After collection of baseline blood samples a 3h infusion of tracers as described below will be started. Relative rates of V_{PC}/V_{CS} will be assessed using a constant

infusion of [$3-^{13}\text{C}$] lactate (8.7 $\mu\text{mol}/[\text{Kg}\cdot\text{min}]$, 99% APE) and rates of glucose production will be measured using a primed/constant infusion of [2H_7]glucose (42 mg/m^2 - 0.84 $\text{mg}/[\text{m}^2\cdot\text{min}]$, 99% APE) (Perry et al. *Nature Communication* 2017). Rates of hepatic ketogenesis will be measured using a constant infusion of [$^{13}\text{C}_4$]βOHB [10 $\mu\text{g}/(\text{Kg}\cdot\text{min})$, 99% APE] as previously described (Perry et al. *Cell Metabolism* 2017). This protocol has been approved the Yale Human Investigation Committee (#20997).

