GC/MS Method for Quantifying [$^{13}\text{C}_4$]β OHB turnover: Analysis of the ^{13}C -enrichment in βOHB will be performed by GC-MS. Samples (100 μL plasma) will be dried under N_2 gas and derivatized with 200 μL n- butanol 4N HCl, then heated for 60 min at 65°C and dried under N_2 gas. The samples will next be reacted with 100 μL of trifluoroacetic acid (Thermo Fisher Scientific)-methylene chloride (Sigma) (1:7). [$^{13}\text{C}_4$]βOHB enrichment will be measured by GC-MS (CI mode, m/z 257 [m+0] and 261 [m+4]).

Whole body energy expenditure, VO_2 , VCO_2 , respiratory quotient assessed by indirect calorimetry: Rates of total-body glucose and lipid oxidation and energy expenditure will be calculated from rates of O_2 consumption and CO_2 production measured during continuous indirect calorimetry.

This trial is registered at CT.gov: NCT 03965130

References

Treatment

- List the clinical dosage/dosage form, route, and dose regimen:

Glucagon will be infused intravenously at rate of 3 ng/(kg·min) for three hours.

Collateral Research

- Include biomarkers, PK, etc.

Plasma samples will be collected at the end of each infusion study and banked for future metabolomic analyses to determine if any plasma metabolites track with glucagon-stimulated rates of hepatic mitochondrial oxidation and/or pyruvate carboxylase flux.

Statistical Plans

- Include justification for clinical sample size and primary hypothesis testing:

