A group size of 12 subjects was determined based on power calculations to detect a moderate to large difference in the effects of glucagon on rates of hepatic mitochondrial oxidation (V_{CS}). The key endpoints will be to determine if glucagon treatment results in significant differences in: 1) rates of hepatic mitochondrial oxidation, 2) rates of hepatic pyruvate carboxylase flux (V_{PC}), 3) rates of hepatic glucose production, and 4) rates of hepatic β-OHB turnover. Statistical differences in these

parameters (within the same individuals) for saline vs. glucagon treatment will be assessed by paired t-tests.

Budget Summary

- Please be sure to complete budget template (excel document)

| | |
|---|---|
| Total Amount Requested: (Include overhead) | \$1,295,423 (including 30% Yale overhead) |
| Additional sources of funding required? (Yes/No) If Yes, please be specific. | No |

Timelines and Study Plans

| | |
|-------------------------------------|---|
| Number of Sites: | 1 |
| Site Names: | Yale Center for Clinical Investigation, Hospital Research Unit |
| Study Start Date: | July 1, 2019 |
| Study End Date: | June 30, 2020 |
| Number of Subjects: | 10 |
| First Patient In Date: | July 1, 2019 |
| Last Patient Out Date: | May 30, 2020 |
| Enrollment Period in Months: | 11 |

Publication Plan

| | |
|---|--|
| Where are you planning to submit for publication? (journals, etc): | Cell Metabolism, Journal of Clinical Investigation, Nature Medicine, PNAS |
| Are you planning to present your data at a scientific meeting? | |
| Please list your target date for submission of publication. | Approximately 2020 |

Drug Supply Information

| | |
|--|-------------------------------|
| Drug Supplies Required (Yes/No)? | No |
| List Drug Supplies and Amount Required: | Drug Name: Amount: |
| List Drug Supplies and Amount Required: | Drug Name: Amount: |
| Placebo Required (Yes/No)? | No |

| | |
|---|----|
| Additional Sources of Drug Supply (Yes/No). If Yes, please specify | No |
|---|----|

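### Do four key endpoints, each with its own paired t-test and none declared primary, leave the study's main claim unprotected?

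*Combined protocol and SAP*

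**What the plan says.** In the Statistical Plans section the form asks the applicant to "Include justification for clinical sample size and primary hypothesis testing". The answer bases the group size of 12 on "power calculations to detect a moderate to large difference in the effects of glucagon on rates of hepatic mitochondrial oxidation", that is, on V_CS alone. It continues: "The key endpoints will be to determine if glucagon treatment results in significant differences in: 1) rates of hepatic mitochondrial oxidation". Pyruvate carboxylase flux (V_PC) comes second, and the list ends with "3) rates of hepatic glucose production, and 4) rates of hepatic" β-OHB turnover. The analysis is one sentence: differences in these "parameters (within the same individuals) for saline vs. glucagon treatment will be assessed by paired t-tests".

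The Hypothesis section answers the prompt "List the clinical Hypotheses in order of priority" with three entries: V_CS, V_PC, and then β-OHB turnover ("3. A physiological increase in plasma glucagon concentrations will promote a significant increase in rates of" labelled β-OHB turnover). Hepatic glucose production has no numbered hypothesis. It does fall under the general objective, "To examine the effects of glucagon on hepatic glucose and fat metabolism", and the Study Design/Clinical Plan section gives it its own glucose tracer.

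The form states no significance level, sidedness, testing order or adjustment, and it does not label any endpoint primary or secondary.

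**The concern.** The form asks for the primary hypothesis test, and the answer gives four tests under one heading. The hypotheses were ranked, but the ranking is not carried into the testing. Glucose production, which has no ranked hypothesis, is even listed above β-OHB turnover, which has one.

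The case to worry about is the one where V_CS is not significant and another endpoint is. The plan does not say whether that second result would be a confirmed finding or a supporting one. If it were presented as the study's success, the false-positive rate behind the claim would exceed that of a single test.

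**Working it through.** **1. Is V_CS set apart in the text?**

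| Place | Position of V_CS |
|---|---|
| Hypothesis section (ranked by priority) | 1 of 3 |
| Statistical Plans, list of key endpoints | 1 of 4 |
| Statistical Plans, sample size | the only endpoint used |

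All three agree. The label is missing, but the ordering is not.

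**2. Can the stated figure of 12 be reproduced?** Not strictly, because significance level, sidedness, power, mean difference and SD are not given. Let dz be the mean paired difference divided by the SD of the paired differences. Power then comes from the noncentral t distribution with n − 1 degrees of freedom and noncentrality dz·√n. At 80% power and a 5% level, n = 12 results from dz = 0.9 two-sided or dz = 0.8 one-sided. So 12 is compatible with one test of V_CS at the full 5%.

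**3. Error rate for V_CS.** It is tested once, by its own paired t-test. At an assumed two-sided 5% its false-positive rate is 5%, however many other endpoints are tested.

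**4. Error rate if any of the four counted as success.** This rule is not in the plan; it is used here to size the worst reading. Assume two-sided 5% per test and no effect on any endpoint.

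- Independent tests: 1 − 0.95⁴ = 1 − 0.8145 = 18.5%.
- Limit under any dependence: 4 × 0.05 = 20%.
- V_CS not significant but another endpoint falsely significant, independent tests: 0.95 × (1 − 0.95³) = 0.95 × 0.1426 = 13.5%.

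The documents give no correlations. Simulation of 400,000 null trials with n = 12 and a common correlation between endpoints gives:

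| Correlation | Any of four significant | V_CS not significant, another significant |
|---|---|---|
| 0 | 18.5% | 13.5% |
| 0.5 | 16.0% | 10.9% |
| 0.7 | 13.6% | 8.6% |
| 0.9 | 9.8% | 4.8% |

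The columns differ by about 5 points throughout, which is the V_CS error rate. With one-sided 2.5% tests the first column runs from 9.6% (correlation 0) to 4.9% (0.9).

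Independence is an unlikely case. The Background and Objectives sections describe one linked pathway: acetyl-CoA activates pyruvate carboxylase, that flux drives gluconeogenesis, and β-OHB turnover stands in for acetyl-CoA. The ratio of V_PC to V_CS also comes from a single lactate tracer.

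**5. What formal control would cost.** Take the sequence V_CS, V_PC, β-OHB turnover, stopping at the first non-significant result. V_CS keeps its unadjusted power. With n = 12, two-sided 5%, the same assumed dz for every endpoint and correlations from 0 to 0.9 (300,000 simulated trials):

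| dz | Unadjusted power | V_PC in sequence | β-OHB in sequence |
|---|---|---|---|
| 0.5 | 35.3% | 12.5–28.0% | 4.4–24.6% |
| 0.8 | 71.4% | 51.1–64.9% | 36.4–61.2% |
| 1.0 | 88.3% | 78.1–84.5% | 68.9–82.3% |

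Check at dz 0.8 and correlation 0: 0.714² = 0.510 and 0.714³ = 0.364.

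Bonferroni over four endpoints (0.05/4 = 0.0125 each) would also hurt V_CS. At dz = 0.89 its power falls from 80% to 56%, and 18 subjects would be needed to restore 80%.

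These power figures use n = 12. The timelines table shows 10, a separate discrepancy; at n = 10 the unadjusted power at dz 0.8 is 62%.

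**The case for a change.** The best argument for a change is that inferring a primary endpoint is weaker than declaring one, and some of the text points the other way. The study title and the design overview give mitochondrial oxidation and pyruvate carboxylase flux equal standing, and all four endpoints are called key. The troublesome outcome is not remote: at dz = 0.8, V_CS would miss significance in about 29% of trials (100 − 71) even with a real effect. The Background section also draws implications for dual-agonist treatment that rest on mitochondrial oxidation, so a miss on V_CS matters. One sentence of labelling, with the other endpoints reported as estimates and 95% confidence intervals, would cost nothing.

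Part of this stands. The status of V_PC, glucose production and β-OHB turnover is unwritten, and the place of glucose production in the list is unexplained.

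The harm does not follow. A reader who sees V_CS fail knows that the first-priority hypothesis, the one the study was sized for, has failed. Nothing in the form lets another endpoint take its place, and no treatment or regulatory decision is tied to any of the tests; Indication and Phase are both entered as not applicable. The free remedy is free because it changes no estimate, p-value or sample size.

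**Conclusion.** The observation is accurate, but it does not call for a change. Followed as written, the plan gives four individually valid paired comparisons, with V_CS marked as the leading one by rank, position and sizing. Its error rate is 5% under the assumed two-sided level. The inflation to between 9.8% and 18.5% needs three things the documents do not supply: a rule that any one positive counts as success, a 5% level for each test, and the absence of any effect on all four endpoints.

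The missing primary label is a gap that analysts will fill the same way. The fixed sequence is the only remedy considered here that would alter conclusions while leaving V_CS's power intact. At dz 0.8 it takes 10 to 35 percentage points of power from β-OHB turnover (71.4 − 61.2 to 71.4 − 36.4), and it moves last or demotes glucose production, which the investigators listed as key. For a 12-subject mechanistic study that is a matter of judgement, and leaving the plan as it stands is a fair choice. The dz values and correlations are assumptions, because the form says only that the effect is moderate to large.

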Investigator Studies Program Review Committee (MISP-RC)

IIS Clinical Concept Form

All fields are required, an incomplete form will be returned to the submitter. If a field is not completed, please note the reason.

Proposed Study Title

| | |
|---------------|---|
| Study Title: | The effect of glucagon on rates of hepatic mitochondrial oxidation and pyruvate carboxylase flux in man assessed by Positional Isotopomer NMR Tracer Analysis (PINTA) |
| Request Date: | July 1, 2019 |

Principal Investigator Contact Information

| | |
|---------------|--|
| Names: | [name] [name]. |
| Title: | Professor of Medicine |
| Address 1 | Yale University School of Medicine |
| Address 2 | [name] |
| City, ST, Zip | [name] |
| Phone/Fax: | [contact] |
| E-mail: | [contact] , |

Institution Contact Information

| | |
|---------------|---|
| Name: | [name] |
| Address 1 | Office of Sponsored Projects |
| Address 2 | [name] |
| City, ST, Zip | [name] |
| Phone/Fax: | [contact] |
| website | https://your.yale.edu/research-support/office-sponsored-projects |

Contracting Information (if applicable)

| | |
|-------|-----|
| Name: | N/A |
|-------|-----|

Study Information

| | |
|---------------------|-----|
| Indication | N/A |
| Phase: | N/A |
| Number of Subjects: | 12 |

Background and Rationale

- Provide background on unanswered question(s) the study is attempting to answer (do not exceed one page)

While it is well-established that alterations in the portal vein insulin/glucagon ratio play a major role in causing dysregulated hepatic glucose metabolism in type 2 diabetes (T2D), the cellular and molecular mechanisms by which glucagon promotes alterations in hepatic glucose production and mitochondrial oxidation remain poorly understood. This is borne out by the fact that both glucagon agonists and glucagon antagonists are being developed to treat T2D, with unclear mechanisms of action.

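### The timelines table plans 10 subjects, but the other five statements of sample size, including the one resting on power calculations, give 12

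*Combined protocol and SAP*

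**What the plan says.** The form states the number of subjects six times.

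| Place | Statement | N |
|---|---|---|
| Study Information table | "Number of Subjects: | 12" | 12 |
| Study Design/Clinical Plan, opening sentence | "will be examined in 12 healthy subjects (ages 21-65" | 12 |
| Study Design/Clinical Plan, second sentence | "will be assessed in 12 healthy overnight fasted subjects by PINTA" | 12 |
| Study Design/Clinical Plan, PINTA procedure | "Subjects (n=12) will be studied by PINTA under 2 conditions" | 12 |
| Statistical Plans | "A group size of 12 subjects was determined based on power calculations to detect a moderate to large difference in the effects of glucagon" | 12 |
| Timelines and Study Plans table | "Number of Subjects: | 10" | 10 |

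The Statistical Plans entry answers the form's own prompt, "Include justification for clinical sample size and primary hypothesis testing". It is the only one of the six that gives a reason for its number. The timelines table also records "Number of Sites: | 1" and an enrolment period of 11 months. The planned analysis is a paired t-test of saline against glucagon within subjects, and V_CS is first in the priority order under Hypothesis.

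**The concern.** Two tables in one form carry the same row label with different values, and the smaller value sits beside the study dates and enrolment period. Someone scheduling or closing recruitment could reasonably work from that table. If they did, recruitment would stop two subjects short of the number the plan ties to its power calculations, and the comparison for the first-priority hypothesis would lose precision and power. With so small a sample, two subjects are a noticeable share of the information. The contradiction would also leave open, after the fact, whether a study that stopped at 10 had reached its planned size.

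**Working it through.** **1. Can the two numbers be reconciled from the text?**

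- *One site's share of a larger total:* no. The same table lists a single site.
- *Subjects per arm:* no. Every subject is studied under both conditions.
- *Completers against enrolled:* not stated. Arithmetically, 10 completers would need 10/(1 − 0.10) = 11.1, rounded up to 12, at 10% dropout, and 10/(1 − 1/6) = 12 at 16.7%. But the form gives no dropout rate and mentions neither replacement nor completers, and it ties 12 itself to the power calculations.
- *Superseded or illegible text:* no. Both entries are current and readable.

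**2. Can the plan's own 12 be reproduced?** No. Statistical Plans gives no alpha, sidedness, target power, numerical effect or SD of the paired differences. What follows compares 10 with 12; it does not validate 12.

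**3. Consequences that need no assumed power or effect size**

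- Pairs: 10 against 12, a shortfall of 2/12 = 17%.
- Infusion studies, two per subject: 20 against 24.
- Half-width of the 95% confidence interval for the mean paired difference, in units of the SD of the paired differences, is t(0.975, n − 1)/√n:
  - n = 12: 2.201/√12 = 0.635
  - n = 10: 2.262/√10 = 0.715
  - ratio 0.715/0.635 = 1.126, so about 13% wider.
- Recruitment rate over 11 months: 10/11 = 0.91 subjects per month against 12/11 = 1.09.

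**4. Power, conditional on assumptions**

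For a paired t-test with standardised paired difference d, power comes from the noncentral t distribution with n − 1 degrees of freedom and noncentrality d√n. Alpha of 5% is assumed throughout.

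First, suppose 12 pairs were sized for a conventional power. Solve for d at n = 12, then evaluate at n = 10:

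| Assumed power at 12 | Test | d | Power at 10 |
|---|---|---|---|
| 80% | two-sided | 0.889 | 70.6% |
| 80% | one-sided | 0.766 | 72.3% |
| 90% | two-sided | 1.029 | 82.5% |
| 90% | one-sided | 0.903 | 83.8% |

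Second, suppose the plan's verbal effect size means d from 0.5 to 0.8:

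| d | Test | Power at 12 | Power at 10 |
|---|---|---|---|
| 0.5 | two-sided | 35.3% | 29.3% |
| 0.8 | two-sided | 71.4% | 61.6% |
| 0.5 | one-sided | 49.2% | 42.7% |
| 0.8 | one-sided | 82.9% | 75.4% |

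Across both tables the smallest loss is 6.0 points (d = 0.5, two-sided) and the largest 9.7 points before rounding (d = 0.8, two-sided). A simulation of 400,000 runs for the two-sided cases agreed with the exact values to within about 0.2 percentage points.

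**The case against.** The strongest reply is that this is a slip in an administrative table. Every scientific section says 12, a reader meeting five statements against one would probably guess correctly, and harm follows only if someone acts on the odd cell. The document is also a concept form. It says the protocol has separate ethics committee approval and refers to a separate budget template; neither is available here, so which number governs recruitment or funding cannot be settled. Finally, the power losses rest on assumed inputs, and the rationale for 12 is itself a bare assertion.

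Much of this stands. The text does not prove that 12 is intended; it only makes 12 much the more likely. The power figures are illustrations. If the verbal effect size means d of 0.5 to 0.8, 12 pairs would have only 35% to 71% two-sided power, so the undocumented power basis matters more than the two-subject gap. The change in recruitment rate is small and shows no feasibility problem.

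None of it removes the contradiction. Planned sample size is a quantity the trial relies on, and a reader should not have to infer it by majority. The loss of precision in step 3 does not depend on the disputed power assumptions.

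**Conclusion.** The concern holds. The form gives two planned sample sizes, 12 in five places and 10 in one, with nothing to reconcile them. The direct consequence of following the timelines table is two fewer pairs and a confidence interval for the V_CS difference about 13% wider, taking the SD of the paired differences as equal. The loss of power is 6 to 10 percentage points, subject to the assumed 5% alpha and the assumed target powers or effect sizes. This should be corrected: the effect is modest, but it bears on a core design figure. That 12 is intended is an inference from the weight of the statements and the power sentence.

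**What to change.** Reconcile the numbers. If 12 is intended, as appears likely, change the timelines entry from 10 to 12 and check that the 11-month enrolment period, and the separate budget template, allow for 12 subjects and 24 infusion studies. The cost is one table cell and that check.

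If 10 is intended, correct all five statements of 12 and, in Statistical Plans, restate the power basis for 10 pairs with its alpha, sidedness, target power, effect and SD of paired differences.

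If 12 means enrolled and 10 means expected completers, say so, state the dropout assumption, and make clear which number the power calculation refers to.
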